11.3 Other considerations

1. Volumetric criteria are currently experimental and the existing data is not strong enough to support the universal requirement of volumetric response criteria in clinical trials. Nevertheless, the RANO-BM working group believes that assessment and reporting of volumetric data and response will further research in this future and encourage its inclusion as a secondary endpoint when feasible. For investigators choosing to report volumetric response data, please note the following recommendations.
 - i. Partial volumetric response should be defined as 65% or greater decrease in the sum volume of CNS target lesions, in addition to the corticosteroid and clinical status criteria outlined previously.
 - ii. Volumetric response should be reported as a waterfall plot to provide a global sense of potential efficacy.
2. Response of non-CNS (extracranial) disease should be assessed separately from CNS (intracranial) disease.
3. Please refer to Table 5 for RANO-BM recommendations for bi-compartmental assessment of response, i.e. when considering local control and distant brain failure separately.

Table 4. Summary of the response criteria for CNS metastases proposed by RANO-BM

	Complete response	Partial response	Stable disease	Progressive disease
Target lesions	None	≥ 30% decrease in sum longest distance	< 30% decrease relative to baseline but < 20% increase in sum longest distance relative to baseline	≥ 20% increase in sum longest distance relative to nadir*

		relative to baseline		
Non-target lesions	None	Stable or improved	Stable or improved	Unequivocal progressive disease
New lesion(s)^	None	None	None	Present*
Corticosteroids	None	Stable or decreased	Stable or decreased	Not applicable#
Clinical status	Stable or improved	Stable or improved	Stable or improved	Worse*
Requirement for response	All	All	All	Any#
*Progression occurs when this criterion is met.				
^A new lesion is one that is not present on prior scans and is visible in a minimum of two projections. If a new lesion is equivocal, for example because of its small size, continued therapy can be considered, and follow-up assessment will clarify if the new lesion is new disease. If repeat scans confirm there is definitely a new lesion, progression should be declared using the date of the initial scan showing the new lesion. For immunotherapy-based approaches, new lesions alone do not define progression.				
#Increase in corticosteroids alone will not be taken into account in determining progression in the absence of persistent clinical deterioration.				

Table 5. Sites of inclusion for assessment of bi-compartmental CNS outcomes.

	Local CNS lesions	Distant CNS lesions	Non-CNS lesions*
Bi-compartmental progression-free survival*	x	X	X
CNS progression-free survival	x	X	
Non-CNS progression-free survival*			X
CNS_{local} progression-free survival	x		

*Non-CNS disease is not assessed in the current protocol.

11. RADIATION NECROSIS

12.1 Radiographic Radiation Necrosis

Assessment for radiation necrosis will be done based on the contrast-enhanced, FLAIR, Diffusion tensor imaging (DTI) and Perfusion weighted imaging (PWI) MRI sequences. Radiation necrosis is typically a contrast enhancing lesion with surrounding edema noted on contrast-enhanced MRI and FLAIR respectively; however, this is difficult to distinguish from recurrent tumor. Therefore, DTI and PWI sequences will be analyzed as well. DTI uses fractional anisotropy that reflects the preferential direction of water diffusion along white matter tracks. Fractional anisotropy in radiation necrosis is lower than that for recurrent tumor due to lack of normal axonal fibers or cells within the necrotic area as compared to partially functioning axonal fibers and cells associated with recurrent tumor (Shah et al., 2012). PWI

assesses intra-lesional and peri-lesional cerebral blood volume. Recurrent tumor is more likely to be associated with higher cerebral blood volume than radiation necrosis as radiation necrosis is devoid of vasculature. The percentage of signal recovery $\geq 76.3\%$ has a sensitivity of 96% and specificity of 100% for radiation necrosis as noted on PWI. (Barajas et al., 2009).

12.2 Symptomatic Radiation Necrosis

Assessment for symptomatic radiation necrosis will be performed based on patients meeting criteria for radiographic radiation necrosis who require steroid administration, bevacizumab, and/or operative resection to treat symptomatic cerebral edema. These will be assessed at each post-SRS follow-up visit in conjunction with Brain MRIs.

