This is not a trivial consideration, as up to 1 in 5 patients treated with SRS for metastatic brain disease may develop symptomatic radionecrosis. This toxicity has the potential to affect outcomes in this patient population, given the proven association between steroid use and poorer overall survival for patients on ICI (Kotecha et al., 2019), and the side effect profile of bevacizumab when used to address symptoms. The paucity of studies examining symptomatic radiation necrosis following SRS in brain metastasis patients who are receiving immunotherapy is further exacerbated by the lack of detail in the literature regarding radionecrosis rates relative to immunotherapy and SRS administration, and the dearth of prospectively collected data (Lehrer et al., 2019). To date, only one study has reported the time from SRS to radiographic radiation necrosis rate (median: 14.7 months), with no studies reporting the time from SRS to symptomatic radiation necrosis (Skrepnik et al., 2017).

Proposed Solution to Metastatic Brain Disease Treatment-Related Morbidity

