4.2 Secondary Outcome Measure

1. 6 month local control, defined as a 6-month rate of any new, recurrent or progressing (as defined by RANO criteria) tumor within the planning target volume compared to pre-SRS on any post-treatment MRI by 6 months. Follow-up MRIs will be fused with the planning scan for this assessment.
2. 6 month radiographic radiation necrosis, defined as brain imaging findings (MRI, MR Perfusion, MR Spectroscopy, and/or PET) consistent with radiation necrosis.
3. 12 month local control
4. 12 month symptomatic radiation necrosis
5. 12 month radiographic radiation necrosis
6. Evaluation of 12 month local control rate by SRS modality (Gamma Knife versus Linear Accelerator)
7. Evaluation of 12 month local control rate by single agent versus multi-agent ICI
8. Evaluation of 12 month local control rate by melanoma versus non-melanoma brain metastases
9. Evaluation of 12 month symptomatic radiation necrosis rate by SRS modality (Gamma Knife versus Linear Accelerator)
10. Evaluation of 12 month symptomatic radiation necrosis rate by single agent versus multi-agent ICI
11. Evaluation of 12 month symptomatic radiation necrosis rate by melanoma versus non-melanoma brain metastases

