5.2 Exclusion Criteria

1. Major medical illnesses or psychiatric impairments, which in the investigator's opinion will prevent administration or completion of the protocol therapy and/or interfere with follow-up
2. Patients unable to receive MRI Brain
3. Patients with more than 10 brain metastases on MRI Brain
4. Any lesion > 4 cm maximum diameter
5. Total volume of metastatic disease more than 30 cm³
6. Previous whole brain radiation therapy
7. For Cohort 1: Previous stereotactic radiosurgery where the 50% isodose line overlaps with current treatment field
8. For Cohort 2: Patients whose treatment will have a dose overlap within the target from prior treatments of 20% or greater
9. Already receiving chronic dexamethasone (chronic = \geq 2 weeks) prior to SRS
10. Not a radiosurgical candidate per Radiation Oncology discretion
11. Existing autoimmune disease
12. Patients who have an unknown primary
13. Histology not amenable for SRS (i.e. lymphoma). (Small Cell Lung Cancer IS amenable.)

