For patients with multiple brain metastases, stereotactic radiosurgery will be delivered to each lesion that has not previously undergone stereotactic radiosurgery. The prescribed dose will be according to the RADREMI dosing schema as described in Table 1 above. Due to the volumetric summation constraint for the remaining metastases, no single lesion greater than 4cm will be allowed on study, and, therefore, the above dose prescriptions can be used. If any two lesions are within 0.8 to 2 cm of each other, the intervening midplane dose will not exceed 13 Gy. This may require treating each respective target with a lesser dose than dictated by the above table. This is designated to minimize toxicity in patients.

Isodose distributions must be calculated, and the prescription isodose line clearly designated, for each target lesion in all planes.

Table 2: Critical Structures [36]

Structure	Maximum critical volume above threshold	Threshold dose (Gy)	Max Point Dose (Gy)
Optic pathway	<0.2 cc	8	10
Brainstem	<0.5 cc	10	15
Cochlea	N/A	N/A	9
Medulla	<1.2 cc	7	

The dose to the above structures must meet constraints as designated by TG-101; the small size of the cochlea allows for only a max point dose and not a maximum critical volume above threshold or a threshold dose (Benedict et al., 2010). If the above constraints cannot be met utilizing the prescribed radiosurgery dose Table 1, then the highest dose to the target volume will be used such that constraints can be met. This will be considered a minor deviation.

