14.4 Sample Size

An optimum one-stage design is planned. We specify a historical 6 month symptomatic radiation necrosis rate of 16% and an expected 6 month symptomatic radiation necrosis rate of 5%. Then, to achieve a power of 80% and control the type I error below 10%, a total of 40 patients evaluable for symptomatic radiation necrosis will be enrolled in the study. If at most 4 patients will experience symptomatic radiation necrosis in 6 months, the proposed dose reduction is claimed to be desirable. Otherwise, it is undesirable. We assume that at most 5% of the patients will not be evaluable for symptomatic radiation necrosis, which results in a total sample size of 42. In addition, we will add an interim analysis for the 6 month local control rate. When 20 patients have been enrolled in the study with their local control outcome being available, we will conduct a binomial exact test for the null hypothesis that the proposed method can maintain a 6 month local control rate of at least 75%. If p-value of this binomial test is less than 0.05, we will reject the null hypothesis and terminate this study earlier for futility.

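### The primary necrosis event has no location limit, so symptomatic necrosis at a site irradiated before entry can be counted against the reduced dose

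*Combined protocol and SAP*

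**What the plan says.** **Event definition.** Sections 3.1, 4.1 and 12.2 define symptomatic radiation necrosis per patient, as imaging consistent with necrosis plus symptoms that need treatment. Section 12.2 counts "patients meeting criteria for radiographic radiation necrosis who require steroid administration, bevacizumab, and/or operative resection to treat symptomatic cerebral edema". Section 12.1 (radiographic criteria) and Section 14.7 (analysis) add no location criterion. Section 4.1 says that follow-up MRIs are fused with the planning scan for the assessment, and goes no further.

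**Local control.** Section 4.2 item 1 carries the same fusion sentence but also sets a boundary: "tumor within the planning target volume compared to pre-SRS on any post-treatment MRI by 6 months".

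**Who may enter.** Whole brain radiotherapy before entry is excluded. Earlier radiosurgery is excluded in Cohort 1 only in this case: "Previous stereotactic radiosurgery where the 50% isodose line overlaps with current treatment field". The Treatment Dose and Delivery text says that "stereotactic radiosurgery will be delivered to each lesion that has not previously undergone stereotactic radiosurgery", which presupposes that some patients have lesions treated earlier.

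**Timing.** Section 2 says that "only one study has reported the time from SRS to radiographic radiation necrosis rate (median: 14.7 months", and adds that no study gives the time to symptomatic necrosis.

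**Decision rule.** Section 14.4 plans 40 evaluable patients, compares a 16% historical rate with a 5% expected rate, and calls the dose reduction desirable if at most 4 patients have the event within 6 months.

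**The concern.** The trial asks whether reduced-dose radiosurgery with concurrent immunotherapy causes less symptomatic necrosis. The event that answers this should arise where the reduced dose was given. As written, a patient whose study lesions are clear but who has treated, symptomatic necrosis at a site irradiated before entry meets the definition. An assessor could set that event aside by using the fused scan, or could count it; the text supports either. In an unblinded single-arm trial with a limit of 4 events, that choice should not be left until the events are known.

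The same definition feeds the 12-month symptomatic necrosis comparisons by modality, immunotherapy type and histology. It also affects Cohort 2 entry, because Section 8.1 requires that no endpoint event has occurred in Cohort 1.

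**Working it through.** **1. The plan's own figure.** The inputs are from Section 14.4: "We specify a historical 6 month symptomatic radiation necrosis rate of 16"%, "an expected 6 month symptomatic radiation necrosis rate of 5"%, and "to achieve a power of 80% and control the type I error below 10"%. With X ~ Binomial(n, p), the smallest n that has P(X ≤ c | 0.16) < 0.10 and P(X ≤ c | 0.05) ≥ 0.80 is n = 40, with c = 3 (type I error 0.098, power 0.862). So 40 is reproduced. The written limit of 4 events gives type I error 0.211 and power 0.952. That mismatch is a separate issue; both limits are shown below so that this point does not depend on it.

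**2. Adding old-site events.** Let f be the share of patients with earlier radiosurgery and r their chance of symptomatic necrosis at the old site within the 6-month window. The documents give neither, so both are assumptions. If old-site and study-site events are independent and the true study-lesion rate is 5%:

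- probability that a patient is counted: p = 1 − (1 − 0.05)(1 − f·r)
- expected patients with an old-site event: 40·f·r (before allowing for the few who also have a study-lesion event)

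| f x r | f·r | p | 40·f·r | P(X ≤ 4) | P(X ≤ 3) |
|---|---|---|---|---|---|
| none | 0 | 0.0500 | 0 | 0.952 | 0.862 |
| 10% x 5% | 0.005 | 0.0548 | 0.2 | 0.934 | 0.826 |
| 25% x 10% | 0.025 | 0.0738 | 1.0 | 0.830 | 0.659 |
| 40% x 20% | 0.080 | 0.1260 | 3.2 | 0.421 | 0.241 |

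For the middle row, p = 1 − 0.95 x 0.975 = 0.0738.

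**3. Where planned power is lost.** Under the limit of 4, power first drops below 80% at about f·r = 3% (0.798; 0.861 at 2%). Under the limit of 3 it is already below 80% at f·r = 1% (0.787).

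**4. Direction.** If the true study-lesion rate is 16% and f·r = 3%, then p = 1 − 0.84 x 0.97 = 0.185, and P(X ≤ 4) falls from 0.211 to 0.114. Added events make a success claim less likely whatever the true rate.

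**5. Effect of the fix.** Limiting the event to study-treated volumes sets f·r to 0. It restores the first row and leaves 40 evaluable patients.

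**The case against.** **Intent is visible.** The overview, the Section 2 summary, Section 6 and Section 14.7 all describe necrosis following, or with, the study radiosurgery. Section 2 describes the toxicity as arising at the irradiated site. The natural purpose of fusing scans is to locate a finding relative to the treated targets. This stands in part: a reader might infer that old-site necrosis will certainly be charged to the study dose, and the documents do not support that. They support only that it can be. Intent is still not a counting rule, and Section 4.2 shows that the authors stated a boundary for local control beside the same fusion sentence.

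**Latency.** A reader might infer from 14.7 months that earlier lesions pass through their peak risk during the study window. That does not follow. The figure is for radiographic necrosis, comes from one study, and the dates of earlier treatment are unknown. It makes such events plausible and no more. Exclusion of patients already on dexamethasone for 2 weeks or longer also removes some with active symptomatic edema at entry.

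**Repeat or salvage treatment.** A reader might extend the point to necrosis after later radiation. The only retreatment described is Cohort 2, which uses the same procedures and dose table, so its necrosis is still necrosis from the study schedule. What is open there is which course and which 6-month clock owns the event. For off-protocol salvage there is only silence.

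**Size and benchmark.** The low-end effect is negligible, and the middle case stays above 80% power under the written limit. The 20% used at the extreme equals the highest overall per-patient rate cited in Section 2. The documents also do not say whether the 16% per-patient benchmark was limited to treated lesions. If it counted all sites, narrowing only the trial's event would favour the reduced dose. All of this stands; it lowers the severity and is the reason for an all-sites sensitivity analysis.

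**Conclusion.** The definition is broader than the question it serves, and this should be fixed. The text alone establishes three things: the event has no location limit, patients with non-overlapping earlier radiosurgery are eligible, and fusion is not tied to a rule for counting.

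The consequence is one-sided, namely an overstated rate for the reduced dose and a greater chance of rejecting a schedule that meets its target. False success does not follow. The size cannot be fixed from the documents. It runs from negligible to a loss of about half the power (0.952 to 0.421), and the upper end needs assumptions that should be read as extreme. A reader might also infer that the 12-month group comparisons are distorted. They are exposed, but nothing shows that earlier radiosurgery differs between the groups.

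**What to change.** - In Sections 3.1, 4.1 and 12.2, define the primary event as symptomatic necrosis within or contiguous with a target volume treated on this protocol, as located on the fused planning scan. Do not tie it to the Table 1 dose, because the Treatment Dose and Delivery text allows lower delivered doses near neighbouring lesions or critical structures.
- Add a lesion identifier to the case report form, with prior and subsequent radiation to that lesion.
- Report necrosis at previously irradiated sites separately, and give an all-sites count as a sensitivity analysis of the primary endpoint.
- For Cohort 2, state which treatment course and which 6-month clock an event belongs to.

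The cost is a few sentences and a short form entry. Fusion is already planned and the sample size does not change. There are two downsides: an occasional judgement on site of origin where fields lie close together, and the uncertainty about what the 16% benchmark counted. The all-sites analysis covers both.

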12. CRITERIA FOR EVALUATION/REMOVAL FROM STUDY

Every subject should be encouraged to remain in the study. Possible reasons for early withdrawal may include, but are not limited to, the following:

1. Withdrawal of consent – Subject decides to withdraw from the study. This decision must be an “independent decision” that is documented in the source documentation
2. Principal Investigator and/or treating physician discretion – The Principal Investigator and/or treating physician may choose to withdraw a subject from the study if there are safety or other concerns.
3. Subject non-compliance.
4. Subject lost to follow-up.
5. Subject enrolled in hospice care.
6. Subject death.

13. STATISTICAL METHODS

14.1 General Considerations

Statistical analysis of this study will be the responsibility of the Department of Biostatistics at Indiana University School of Medicine. Parameter estimates and relevant summary statistics will be reported for both efficacy and safety outcomes. Continuous variables will be summarized by means, medians, minima, maxima and standard deviations. Categorical variables will be summarized by frequencies and percentages. Missing data will not be imputed. Additional exploratory analysis will be conducted when appropriate. Changes from the analysis plan will not require an amendment to the protocol unless it changes a significant feature in the protocol. If any changes occur, they will be documented in the clinical study report. The statistical analysis methods are outline below.

14.2 Study Design

This is a single-arm pilot study without blinding.

14.3 Analysis Datasets

Enrolled Population

The enrolled population comprises all subjects who meet the eligibility criteria and are registered onto the study.

Safety Population

The safety population comprises all subjects who have received at least one dose of radiation. This set will be used for safety analysis.

Efficacy Population

The efficacy population comprises all subjects who have completed stereotactic radiosurgery. This population will be used for efficacy analysis.

14.4 Sample Size

An optimum one-stage design is planned. We specify a historical 6 month symptomatic radiation necrosis rate of 16% and an expected 6 month symptomatic radiation necrosis rate of 5%. Then, to achieve a power of 80% and control the type I error below 10%, a total of 40 patients evaluable for symptomatic radiation necrosis will be enrolled in the study. If at most 4 patients will experience symptomatic radiation necrosis in 6 months, the proposed dose reduction is claimed to be desirable. Otherwise, it is undesirable. We assume that at most 5% of the patients will not be evaluable for symptomatic radiation necrosis, which results in a total sample size of 42. In addition, we will add an interim analysis for the 6 month local control rate. When 20 patients have been enrolled in the study with their local control outcome being available, we will conduct a binomial exact test for the null hypothesis that the proposed method can maintain a 6 month local control rate of at least 75%. If p-value of this binomial test is less than 0.05, we will reject the null hypothesis and terminate this study earlier for futility.

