14.7 Analysis of Primary Objectives

For the primary objective of 6 month symptomatic radiation necrosis for dose-reduced stereotactic radiosurgery concomitant with immunotherapy, the proportion of patients who have symptomatic radiation necrosis at 6 months will be calculated using Kaplan-Meier method along with a 95% confidence interval. Testing the observed proportion smaller than a baseline 6 month symptomatic radiation necrosis rate of 16% at a type I error rate of 5% using a one-sided binomial exact test will be done.

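### The success rule of at most 4 necrosis events in 40 has a 21% type I error, not below 10%, and it disagrees with the 5% exact test in section 14.7

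*Combined protocol and SAP*

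**What the plan says.** Section 14.4 (Sample Size) opens with "An optimum one-stage design is planned". The null and target 6-month rates of symptomatic radiation necrosis are 16% and 5%. The stated error rates and size are "to achieve a power of 80% and control the type I error below 10%, a total of 40 patients evaluable", raised to 42 to allow for 5% non-evaluable. The decision rule is "If at most 4 patients will experience symptomatic radiation necrosis in 6 months, the proposed dose reduction is claimed to be desirable"; with more events the dose reduction is to be called undesirable.

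Section 14.7 (Analysis of Primary Objectives) gives a Kaplan-Meier estimate with a 95% confidence interval. It also tests whether the proportion is below a "baseline 6 month symptomatic radiation necrosis rate of 16% at a type I error rate of 5% using a one-sided binomial exact test".

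No section says whether the event count in 14.4 or the test in 14.7 decides the trial.

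**The concern.** The rates, sample size, error limit and cut-off in 14.4 must be consistent with one another, because any three of them constrain the fourth. Under the null the expected count is 40 × 0.16 = 6.4 events, with standard deviation √(40 × 0.16 × 0.84) = 2.32. A cut-off of 4 lies only about one standard deviation below that mean, which is too close for a tail of less than 10%.

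Section 14.7 then uses a different error level for the same endpoint and the same null rate. The count in 14.4 is the only final success rule in the plan. If its error rate is wrong, or if a second rule gives a different answer, the headline conclusion depends on which section is read.

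**Working it through.** **Inputs.** From 14.4: null rate 0.16, target rate 0.05, n = 40 evaluable, power 80%, type I error below 10%, success at 4 or fewer events. From 14.7: one-sided exact binomial test against 0.16 at 5%.

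**Formula.** With X the number of patients with an event and c the cut-off:
- type I error = P(X ≤ c | n, 0.16)
- power = P(X ≤ c | n, 0.05)
- P(X ≤ c | n, p) = Σ C(n,k) p^k (1−p)^(n−k), summed over k = 0 to c

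**Step 1: reproduce the plan's sample size.** A search over all n and c for type I error below 0.10 and power of at least 0.80 gives n = 40 with c = 3 as the smallest design. The printed 40 is therefore reproduced exactly, but with a cut-off of 3.

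**Step 2: error rate of the printed rule.** At n = 40 and p = 0.16 the probabilities of 0, 1, 2, 3 and 4 events are 0.0009, 0.0071, 0.0265, 0.0639 and 0.1126. They sum to 0.211.

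| Success if events ≤ | Type I error (p = 0.16) | Power (p = 0.05) |
|---|---|---|
| 2 | 0.0345 | 0.677 |
| 3 | 0.0984 | 0.862 |
| 4 (as printed) | 0.2110 | 0.952 |

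**Step 3: does another reading rescue the 4?**
- All 42 patients evaluable: 0.176.
- 38 evaluable: 0.251.
- Normal approximation at n = 40: 0.150 without continuity correction, 0.206 with it.
- A cut-off of 4 first falls below 10% at n = 48 (0.099), or at n = 40 with a null rate of about 19% (0.09995). The plan states neither.

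**Step 4: the test in 14.7.** The one-sided exact p-value for c events in 40 is the type I error column above. Two events give p = 0.035, three give 0.098 and four give 0.211. At 5% the test rejects only at 2 or fewer, and its power at a 5% rate is 67.7%. The smallest design with type I error of at most 5% and power of at least 80% is n = 55 with c = 4 (0.0476 and 0.860).

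**Step 5: how often the two sections disagree.** They disagree at 3 or 4 events.
- True rate 5%: 0.952 − 0.677 = 0.275.
- True rate 16%: 0.2110 − 0.0345 = 0.1765, about 17.6%.

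Correcting the cut-off to 3 while leaving 5% in 14.7 still leaves a disagreement at exactly 3 events, with probability 0.862 − 0.677 = 0.185 at a true rate of 5%.

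**Step 6: what a just-passing result would look like.** The exact 95% confidence interval for 4/40 is 2.8% to 23.7%, which includes the historical 16%.

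**The case against.** No one can fairly dispute the arithmetic, but several points can be raised on the other side.

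- *This is a pilot, and the confidence interval will show the uncertainty.* True, but 14.4 states a numerical error limit and a binary claim. A limit of 10% is already lenient, and the rule as printed does not meet it.
- *There is also an interim stop.* The interim look at 20 patients tests local control, not necrosis. It stops at 11 or fewer controlled, with probability 0.041 if true control is 75%. Assuming independence from necrosis, the overall type I error is still 0.211 × 0.959 = 0.202.
- *The slip may lie elsewhere.* That the cut-off is off by one is an inference. It is a strong one, because 40 is exactly the minimum for a cut-off of 3, but the sponsor should confirm it.
- *The 80% power was never promised for the 5% test.* This stands. Section 14.7 states no power, so the accurate statement is that 40 patients were not sized for a 5% test.
- *Failing to reject at 5% is not the same as calling the dose reduction undesirable.* This also stands. The fault is that one section claims success where the other finds no significant evidence, and neither is given precedence.
- *A fixed cut-off of 3 is fragile.* This stands too. With 39 evaluable patients its type I error is 0.110, with 38 it is 0.122, and with 36 it is 0.151. With 42 it is 0.079. Eligibility asks only for an estimated median survival of at least 6 months, so falling short of 40 is plausible.

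**Conclusion.** The concern holds. As printed, the success rule in 14.4 has an exact type I error of 21.1% against a stated limit of 10%, and no reading of the plan's own inputs brings it under that limit. Separately, 14.4 and 14.7 use different error levels for one endpoint and disagree at 3 or 4 events. That outcome has probability 27.5% if the target rate of 5% is true and 17.6% if the historical rate of 16% is true.

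These figures rest on 40 evaluable patients, independent outcomes between patients, and each patient counted once as event or no event by 6 months. This must be fixed, because it is the final success rule and the error can reverse the trial's conclusion.

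**What to change.** Confirm the intended design, then make the two sections state one rule.

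- **Preferred: keep n = 40 and the 10% level.** In 14.4 set the cut-off at 3 or fewer of 40, and print the exact type I error (9.8%) and power (86.2%). In 14.7 set the one-sided exact test at 10%, so that test and rule coincide.
- **Alternative: keep 5% with n = 40.** State in both sections that success means 2 or fewer of 40, with type I error 3.5% and power 68%.
- **Alternative: keep both 5% and 80% power.** This needs 55 evaluable patients and a cut-off of 4 (type I error 4.8%, power 86.0%).

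Whichever is chosen, say that the cut-off follows from the exact test at the number actually evaluable. Under the 10% level it is 3 for 40 to 42 patients, but 2 for 38 or 39 (type I error 0.045 and 0.039).

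The first two options cost wording changes in two sections and no patients. The preferred one makes success one event stricter than printed. The third adds 15 evaluable patients.
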